14.1.2. Recording Adverse Events

It is the responsibility of the investigator to document all AEs (i.e., PTAEs and TEAEs), with an onset after the subject signs the ICF. For the purpose of this study, all AEs that occur till Day 30 must be recorded regardless of whether or not they are considered related to the study drug. Whenever feasible, AE terms should be documented as medical diagnoses (highest possible level of integration); otherwise, the AEs should be reported separately as individual signs or symptoms. Only one AE per line should be recorded in the AE case report form (CRF); for example, an AE of nausea and vomiting should be listed as two separate events: the event of nausea and the event of vomiting. If a diagnosis is established after symptoms are recorded on the AE CRF, the diagnosis should be recorded and the symptoms collapsed (removed; i.e., lined through and initialed). Whenever possible, abnormal laboratory results should be reported as their clinical corollary (e.g., low potassium should be recorded as hypokalemia).

A continuous AE with varying grades of severity should be recorded as one AE. The highest grade of severity experienced by that subject during the course of the continuous AE should be recorded.

Any condition noted before the subject signs the ICF will be listed as medical history and is considered a pre-existing condition. If a pre-existing condition changes (i.e., becomes more severe or more frequent) at any time after the ICF is signed, or after study drug administration, it is considered an AE. Note: A change in treatment for a pre-existing condition (e.g., new high blood pressure medication) does not necessarily indicate an AE.

Information recorded on the AE CRF will include the AE term, the date and time of onset, severity, seriousness, relationship to study drug, action taken with subject due to an AE, and the outcome of the AE, including the date and time of resolution, if applicable.

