Treatment-emergent adverse events (TEAEs) are those with onset on or after the start time of study drug administration, and before or at the end of the study (expected to be Study Day 30 ± 3 days).

Time 0 (zero)

Time 0 is defined as the time of the end of study drug administration, with the exception of AE's and concomitant medications. Time 0 for AE's and concomitant medications are defined as the time of the start of study drug administration.

Time Deviation

For PK sampling time window, *Time Deviation* is the difference (actual – start/end of target window of assessment) between the actual and target window of assessment in the PK sampling. If sampling occurred before the beginning of target window of assessment, time deviation will be calculated by subtracting the actual time from the beginning of the target window of assessment. If the sampling occurred after the end of target window of assessment, time deviation will be calculated by subtracting the actual sampling time from the end of the target window of assessment. Any samples occurring with the target window will have a time deviation of 0.

Baseline

Baseline measurement or assessment is defined as the last available measurement or assessment prior to the start of study drug administration.

Last Follow-up Time

For subjects who withdraw prematurely, the last follow-up time will be defined as the maximum of the last pain or any other study assessment, the last concomitant medication start or end datetime, and the last adverse event start or end datetime.

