6.1.1.4 Adverse Event Severity or Relationship to Study Drug

If severity of an AE is not reported, then for tables of AEs by severity, the event will be classified as 'Severe'. If relationship to study drug is not reported for an AE, then for tables of study-drug related treatment emergent AEs, the event will be assigned the relationship 'definite'. If the AE starts before study drug administration, then the relationship 'unrelated' is presumed. Tables presenting related AEs will include all AEs with relationships of 'possible', 'probable' or 'definite' as assessed by the investigator.

If severity or relationship is missing, then a sub-row will be added in the summary tables for imputed vs. severe or imputed vs. related.

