6.8.4 Adverse Events

Adverse events will be coded using the Medical Dictionary for Regulatory Activities (MedDRA).

An AE will be considered TEAE if the onset date and time is between the start time of study drug administration and the final Day 30 visit.

If an AE has a partial onset date and time the imputed start and stop dates and times will be used to determine treatment-emergence (e.g., stop date and time is before start time of study drug administration). All AE summaries will present TEAEs only; AEs that are not treatment-emergent will be included in listings but not summarized.

The incidence of subjects reporting TEAEs will be tabulated by the number and percentage of subjects reporting the TEAE. Incidence is defined as a subject reporting at least one TEAE within the summary level. Summary levels are 'at least one TEAE', System Organ Class (SOC) and Preferred Term. Subjects will be counted only once within each reporting level on the table. For example, if a subject reports a TEAE of headache on two separate occasions, the subject will be counted only once in the headache row of the table. Similarly, if a subject reports two separate TEAEs within the same SOC the subject will only be counted once in the summary row for that SOC. A summary of subjects reporting at least one TEAE during the study will also be presented.

The first row on every TEAE table will be the number and percentage of subjects reporting at least one TEAE. Subsequent rows will be presented in descending order of subject counts for the overall within each age group and treatment group, with the most common system organ class first, followed within each SOC by the PT in descending subject count order. For tables presenting the severity or relationship to study treatment of AE, the sort order will be determined by the number and percentage of subjects reporting the PT, thus the sort order of rows will remain the same for the relation or severity tables as the tables by preferred term.

The following summaries will be presented for the AEs reported by the subjects:

An overview of all TEAEs, serious TEAEs and TEAEs of Special Interest will present the number and percentage of subjects in the following categories:

- Any TEAE
 - Maximum severity: Mild
 - o Maximum severity: Moderate
 - Maximum severity: Severe
- At least one related TEAE
- At least one serious TEAE
- At least one TEAE of special interest
- Subjects discontinued due to a TEAE

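### An adverse event that starts between consent and dosing and worsens after dosing is missing from every AE summary table except the deaths row

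*SAP*

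**What the plan says.** SAP Section 4 (Definitions) states: "Treatment-emergent adverse events (TEAEs) are those with onset on or after the start time of study drug administration", up to the end of the study. SAP 6.8.4 repeats the test: "An AE will be considered TEAE if the onset date and time is between the start time of study drug administration" and the last visit. Neither sentence mentions worsening. SAP 6.8.4 then limits what is tabulated: "All AE summaries will present TEAEs only; AEs that are not treatment-emergent will be included in listings but not summarized".

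Protocol 14.1.2 governs recording: "A continuous AE with varying grades of severity should be recorded as one AE", and "The highest grade of severity experienced by that subject during the course of the continuous AE should be recorded". On the form itself, "Information recorded on the AE CRF will include the AE term, the date and time of onset, severity, seriousness, relationship to study drug", followed by action taken, outcome and resolution time. No date for a change of grade is listed.

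The same section treats conditions known before consent differently: "If a pre-existing condition changes (i.e., becomes more severe or more frequent) at any time after the ICF is signed", or after study drug, the change is an AE. Protocol 14.1.1 labels an AE arising between consent and the start of study drug a pre-treatment AE (PTAE), and its general AE definition counts deterioration as well as new onset.

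Where the investigator gives no relationship, SAP 6.1.1.4 adds: "If the AE starts before study drug administration, then the relationship 'unrelated' is presumed".

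**The concern.** The recording rule and the TEAE definition are each workable alone. Together they leave a gap: post-dose worsening of a continuous PTAE has no TEAE record to sit on.

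The gap matters more here than in many trials because study drug is infiltrated near the end of surgery, before wound closure (Protocol 11.1). Anaesthesia and most of the operation therefore fall in the pre-treatment period. Group 2 includes cardiac surgery, and abnormal or irregular heart rate is a listed cardiac AESI. A mild rate disturbance that is still present at infiltration and then worsens is something the AESI tables ought to show.

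Safety is the secondary objective. Protocol 12.4 names the incidence of TEAEs and of SAEs to Day 30 as an endpoint, yet the SAP tabulates only serious TEAEs. An SAE that arises when a PTAE worsens would appear in listings only.

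**Working it through.** The plan gives no expected TEAE rate, so there is no figure to reproduce. The check follows one event through the rules.

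1. *Onset.* The event begins after consent and before the start of study drug. Protocol 14.1.1 makes it a PTAE.
2. *Worsening.* It continues without resolving and becomes severe or serious after dosing. Protocol 14.1.2 keeps one record at the highest grade. One record carries one onset, taken here as the start of the event.
3. *Classification.* That onset precedes the start of study drug, so the event fails both SAP tests.
4. *Tables.* SAP 6.8.4 summarises TEAEs only. The overview, incidence, severity, relationship, serious and AESI tables are all titled as TEAE tables. The exception is the died-on-study row of the overview, which is defined by time from dosing.
5. *Listings.* The all-AE and all-SAE listings include the event, with a pre-dose start and the maximum grade. A reader cannot tell whether that grade was reached before or after dosing. The listing of protocol-defined AESIs shows only term, start and end.

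Neighbouring cases side by side:

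| Course of the event | Can post-dose worsening be a TEAE? |
|---|---|
| Condition noted before consent, worsens after dosing | Yes; the change is an AE in its own right |
| AE begins after consent and before dosing, continuous, worsens after dosing | No, under the one-record rule |
| AE begins before dosing, resolves, recurs after dosing | Yes; it is not continuous, so the one-record rule does not apply |
| AE begins after dosing | Yes |

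Only the second row fails. It also conflicts with two other statements. Protocol 14.1.1 counts deterioration as an AE. SAP Section 3 makes worsening dizziness an AESI, but dizziness that began before dosing and worsened afterwards cannot reach the AESI table.

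Scale: each Group 1 arm has 15 (Part 1) + 15 (Part 2) = 30 planned subjects. One child lost from a row changes it by 1/30 = 3.3 percentage points. A child is counted once per row, so the loss occurs only if that child has no other TEAE in that row. Group 2 columns are split by spine and cardiac surgery. The split is not given, so no Group 2 figure can be stated.

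**The case against.** The strongest reply is that few events can fall in the gap and that those which do are still seen.

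- Protocol 10.2 makes a child ineligible for study drug if a clinically significant event uncovered during surgery might make the child unstable or complicate recovery, and 13.4 requires this to be checked. Such children are not dosed and are outside the Safety Population. This stands. It narrows the gap to milder events still ongoing at infiltration but does not close it.
- The deterioration wording in Protocol 14.1.1 might lead a site to open a new record, and 14.1.2 does not say in terms which onset to enter. This stands as an ambiguity. The specific instruction for a continuous AE is still one record, and sites could follow either text.
- SAEs are reported within 24 hours from consent to Day 30, the DSMB reviews events, and the listings are not confined to TEAEs. This stands: the loss is in tabulation and dating, not in detection.
- A dosing-day AE with no recorded time is given the end time of study drug administration (SAP 6.1.1.3), which makes it a TEAE. That is true, but it concerns missing times, not known pre-dose onsets.

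Stronger readings are tempting, but the documents do not support them:

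- A reader might infer that post-dose worsening vanishes from all safety output. It does not. Vital-sign, neurological and laboratory tables use post-dose data whatever the TEAE status.
- A reader might infer that the presumption of no relationship lowers the count of related events. It changes no current table, because these events are already outside the summaries and the related-event listings are treatment-emergent only. It also never overrides a recorded assessment.
- A reader might put several percentage points of understatement on each arm. That needs a count of affected children, and none is given.

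**Conclusion.** The gap is real and limited. It covers continuous AEs with onset after consent and before the start of study drug that worsen or become serious after dosing. These are absent from every AE summary table except the died-on-study row, and the listings cannot date the worsening. Within this class the effect runs one way: incidence, severity and seriousness can be understated and never overstated.

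The conclusion assumes that sites follow the one-record rule and enter the time the event first began. The size is unknown. The only figure available is the 3.3 points per child in a Group 1 row, under the condition stated above.

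**What to change.** 1. In SAP 4 and 6.8.4, define a TEAE as an AE with onset on or after the start of study drug, or one with earlier onset that increases in severity or becomes serious on or after the start of study drug.
2. In Protocol 14.1.2 and the CRF instructions, require a new AE line, or the date and time of the grade change, when a PTAE worsens after dosing. Reconcile this with the deterioration wording in 14.1.1. The recording change is needed because a SAP edit cannot recover a date that was not collected.
3. As a conforming change, limit the presumption in SAP 6.1.1.4 to pre-dose AEs that do not worsen after dosing. Otherwise it would begin to matter once step 1 is made.
4. For records already collected without a worsening date, count as TEAEs those ongoing at dosing that are graded severe or are serious, or show them in a separate table. Some may have reached that grade before dosing, so the rule should be footnoted.

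The cost is slightly higher TEAE counts, one added clause in two places of the SAP, and a small change to the protocol and CRF instructions. CRF version 4.0 had already been issued when the SAP was written, so step 4 may be needed for part of the data.

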10.3. Removal of Subjects from Therapy or Assessment

Every reasonable effort should be made to maintain subject compliance and participation in the study. Subjects who withdraw from the study after receiving study drug should undergo safety assessments till the end of the study (Day 30).

If a subject who withdraws from the study has an ongoing AE, every effort must be made to follow such events until satisfactory resolution is obtained, or further follow-up is otherwise no longer warranted.

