11.6. Prior and Concomitant Therapy and Medications

All medications taken within 30 days prior to study drug administration till Day 30 after study drug administration or until the subject is withdrawn from the study, whichever is sooner, will be

recorded on the eCRF. Additionally, any medications administered in association with an AE will be recorded till Day 30.

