6.1.1.3 Adverse Event or Concomitant Medications Dates or Times

For AEs or concomitant medications with missing or partially missing start/stop date/time, the following imputation rules will be applied:

For partial start date/time:

- If the year is unknown, then the date will be assigned the year of the first dose of study treatment. If the entire study is conducted within the same year, then that year will be the imputed year.
- If the month is unknown, then, if the year matches the year of the dose of study drug date, then the month and day of the dose of study drug date will be used to impute the missing month and corresponding day. Otherwise, 'January' will be assigned.
- If the day is unknown, then, if the month and year match the month and year of the dose of study drug date, then the day of the dose of study drug date will be imputed. Otherwise, '01' will be assigned.
- If the time is unknown, then, if the date (day, month, and year) matches the date of the administration of study drug, then the end time of the study drug administration will be imputed. Otherwise, '00:00' will be assigned.

For partial stop date/time:

- If the year is unknown, then the date will be assigned the year that subject discontinued from study, and time will be set to the last time of the day ('23:59').
- If the month is unknown, then month subject discontinued from study will be assigned.
- If the day is unknown, then the last day of the month will be assigned.
- If the time is unknown, then the last time of the day will be assigned ('23:59'), with the exception of end times for epoch in any CDISC dataset, where next day and '00:00' would be assigned.

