6.9.2 Opioid Consumption

Opioid medications will be converted to oral morphine equivalent dose (MED mg) using the appropriate conversion factor from Table 8 for all summaries. Opioids are collected on the Post Surgical Pain Medication and Prior/Concomitant Medications eCRF pages. The amount of total opioid dose will be calculated as the sum of the oral morphine equivalent of all opioids taken after surgery up to the timepoint of interest. Subjects with no opioid use during the period in question will be assigned a dose of 0 for summaries and changed to the lesser of 0.1 or half of the smallest total amount observed in the study, whichever is smaller, prior to being transformed with the natural logarithm for analysis. Total postsurgical opioid dose will be calculated through 24, 48, and 72 hours. In addition to the descriptive statistics for continuous data, geometric mean (GM) and coefficient of variation (CV) will also be included and mean and SD will be excluded.

For the calculation of the total dose through 72 hours, if a subject's last follow-up time is 72-x hours, then the approach described in Section 6.1.1.2 is used.

Medication	Unit	Route	Oral Morphine Conversion Multiplication Factor
Morphine, Morphine Sulfate	mg	IV,IM,SC	3
Morphine	mg	РО	1
Morphine	mg	R	1
Buprenorphine	mcg	IM	75
Buprenorphine	mcg	SL	37.5
Codeine (Tylenol 3, acetaminophen-coedine,	mg	РО	0.15
Paracetamol Forte, Tylenol 4,)			
Codeine Phosphate	mg	IM	0.24
Demerol, Meperidine, Pethidine	mg	IV,SC	0.3
Demerol, Meperidine, Pethidine	mg	РО	0.1
Fentanyl, Remifentanil	mcg	IV,PO,IM,TD	300
Hydromorphone	mg	R	4
Hydromorphone (Dilaudid)	mg	IV,IM,SC	20
Hydromorphone (Dilaudid)	mg	РО	4
Hydromorphone (Dilaudid)	mg	EP	45
Ketobemidone, Oxycodone	mg	IV	3
Methadone	mg	IM	3
Methadone	mg	РО	1.5
Methadone	mg	IV	6
Nalbuphine/Nallouphine (Nubain/Manfine)	mg	IV,IM,SC	3
Oxycodone, Oxycocet, Percocet, acetaminophen-	mg	PO	1.5
oxycodone, Oxycodone HCl			
Oxymorphone	mg	РО	3
Oxymorphone	mg	IM,SC	30
Pentazocine/Acetaminophen	mg	РО	0.2
Pentazocine/Naloxone	mg	PO	0.2

Table 8 Oral Morphine Equivalents

Pentazocine	mg	IM	1
Tapentadol	mg	PO	0.3
Ultram, Tramadol, Tramacol hydrochloride	mg	PO,IM	0.25
Vicodin, Norco, Lorcet, Lortab, hydrocodone-	mg	PO	1
acetaminophen, Ketobemidone			

Key: EP = Epidural; IM = Intramuscular; IV = Intravenous; INS = Intra Nasal Spray; NA = Not Applicable; PO = Oral; R = Rectal; SC = Subcutaneous; SL = Sublingual; TBD = To Be Determined; TD = Transdermal

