6.9.2.1 Time to First Postsurgical Use of Opioid Medication

Time to first postsurgical use of opioid rescue medication will be computed in hours as the date and time of the first opioid rescue medication minus the date and time of the end of surgery. If a subject is not administered an opioid rescue medication, the time to first administration will be censored at 72 hours after surgery or at the time of last follow-up, whichever is earliest. Time to first opioid consumption will be summarized by the quartiles (25th, 50th, and 75th), minimum and maximum estimated using Kaplan-Meier methods within age group and part of the study. The quartile and the 95% confidence limits (CONFTYPE=LOGLOG) for each quartile will be presented.

A Kaplan-Meier plot of the time from end of surgery to first opioid rescue medication use will be presented within age group and part of the study, and a log-rank test p-value of treatment difference shown for group 1.

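### Last follow-up time in the SAP is not tied to opioid recording: a child withdrawn opioid-free before 72 h can be censored at 72 h, and SAP 6.9.2 and 6.1.1.2 disagree on when total dose is projected

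*SAP*

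**What the plan says.** **Definition.** In SAP 4, for premature withdrawals, "the last follow-up time will be defined as the maximum of the last pain or any other study assessment", together with "the last concomitant medication start or end datetime, and the last adverse event start or end datetime".

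**Where it is used.** In SAP 6.9.2.1, the time to first opioid of a child given none "will be censored at 72 hours after surgery or at the time of last follow-up, whichever is earliest". In SAP 6.9.2, for the 72 h total, "if a subject's last follow-up time is 72-x hours, then the approach described in Section 6.1.1.2 is used".

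**A second trigger for the total.** SAP 6.1.1.2 calls for projection whenever a subject discontinues before the interval ends, and lists withdrawal among its examples. Its formulas, however, take x as the time of discharge.

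**What is recorded after withdrawal.** Protocol 11.6 records medications "till Day 30 after study drug administration or until the subject is withdrawn from the study, whichever is sooner", with drugs given for an adverse event recorded to Day 30. Protocol 11.6.3 asks for all postsurgical analgesics to 96 h and does not mention withdrawal.

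**What follow-up continues.** Protocol 10.3 says dosed subjects who withdraw should have safety assessments to Day 30, and that ongoing adverse events be followed. Protocol 10.3.2 is weaker: after a final evaluation the subject may be followed.

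**Status.** Protocol 12.6 makes the opioid endpoints exploratory, and Protocol 15.1 rules out formal hypothesis testing. SAP 6.9.2.1 nevertheless shows a log-rank p-value for Group 1.

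**The concern.** A censoring time should mark the end of the period in which the event could have been seen. The event here is a first opioid dose, but the SAP's definition runs to the last contact of any kind. Under Protocol 11.6 routine medication recording can end at withdrawal, while safety visits and adverse event follow-up go on producing dates. Time after withdrawal then counts as opioid-free because nobody was recording, and better safety follow-up makes this more likely.

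The same definition drives projection of the 72 h total in SAP 6.9.2. There a separate rule in SAP 6.1.1.2 points the other way, so two programmers could produce different totals for the same child.

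**Working it through.** **1. The plan's own example.** SAP 6.1.1.2 projects the 72 h total as 72 × D(0,x)/x for x < 36, and as D(0,x) + D(2x−72, x) for 36 ≤ x < 72. For x = 70 the window starts at 2 × 70 − 72 = 68 h, which matches the SAP's example of 68 to 70 h.

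**2. Time to first opioid, one child.** Suppose a child withdraws opioid-free at 24 h and an adverse event resolves on Day 10.

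- Last follow-up under SAP 4 is Day 10, so the censoring time is min(72 h, Day 10) = 72 h.
- If recording stopped at withdrawal, opioid use was observed for 24 h.
- The credited but unobserved time is 72 − 24 = 48 h.

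**3. Effect on the Kaplan-Meier estimate.** The documents give no withdrawal rate, so the following is assumed: an arm of 30 (15 per part, Parts 1 and 2 pooled), 24 first uses before 12 h, k children withdrawn opioid-free at 12 h, and the other 6 − k followed to 72 h, of whom one stays opioid-free.

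- Just before 12 h the estimate is 6/30 = 0.20.
- Censored at 12 h: 6 − k remain at risk and one survives, so S(72) = 0.20 × 1/(6 − k).
- Censored at 72 h: the withdrawn children stay at risk throughout, so S(72) = (1 + k)/30.

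| k | Censored at 12 h | Censored at 72 h | Ratio |
|---|---|---|---|
| 1 | 0.040 | 0.067 | 1.7 |
| 2 | 0.050 | 0.100 | 2.0 |
| 3 | 0.067 | 0.133 | 2.0 |

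The two columns differ only because other children in the arm first use an opioid after 12 h. With no later first uses the estimate would not change.

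**4. Total dose, the two readings.** Suppose 40 mg (oral morphine equivalent) is recorded by withdrawal at 24 h, with the same Day 10 date.

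- SAP 6.9.2 trigger: last follow-up is after 72 h, so there is no projection and the total is 40 mg.
- SAP 6.1.1.2 trigger, with x read as the withdrawal time: 72 × 40/24 = 120 mg, a ratio of 3.
- One such child changes the geometric mean of an arm of 30 by a factor of 3^(1/30) = 1.037, and two by 3^(2/30) = 1.076. In an arm of 15, if parts are analysed separately, one child gives 3^(1/15) = 1.076.
- At a constant rate of use, the unprojected amount is x/72 of the projected one: 17% at 12 h, 33% at 24 h, 50% at 36 h, 67% at 48 h and 83% at 60 h.
- For a child with nothing recorded, 72 × 0/x = 0, so the two readings agree.

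**5. Notation.** SAP 6.9.2 writes last follow-up as 72 − x, whereas x in SAP 6.1.1.2 is the elapsed time itself. Taken literally, last follow-up at 24 h gives x = 48. The second formula then returns D(0,48) + D(24,48) = 40 + 0 = 40 mg, even though projection was triggered.

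**The case against.** A reader might infer that every withdrawn child is counted as observed through 72 h, with unrecorded opioid use taken as none in both endpoints. The documents do not support that, for these reasons.

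- **Total dose.** SAP 6.1.1.2 states that a subject withdrawn before the interval ends gets a projected total. The unprojected result follows only if the trigger in SAP 6.9.2 governs. This stands: for totals the finding is an inconsistency, not an established error. Nor is 120 mg the truth. If use declined as exp(−t/24), the first 24 h would hold 66.5% of the 72 h total, so 40 mg would mean about 40/0.665 = 60 mg.
- **Recording after withdrawal.** Protocol 11.6.3 and footnote 6 to the protocol's Table 1 carry recording to 96 h with no exception for withdrawal, and the Day 7 and Day 30 contacts (Protocol 13.7, 13.8) collect concomitant medications. If these apply after withdrawal and are carried out, use is observed beyond 72 h and censoring there is correct. This stands as a conflict, but Protocol 11.6 is the passage that addresses withdrawal, and it ends recording there.
- **Frequency.** Protocol 10.3.1 discourages ending assessments after a single dose, and 10.3.2 makes later follow-up optional. The censoring error needs a child who is opioid-free at withdrawal, before 72 h after major surgery, with a later date on file. A child who has already taken an opioid is unaffected. This stands: the case is probably uncommon.
- **Imputed dates.** For a partial stop date, SAP 6.1.1.3 says "If the day is unknown, then the last day of the month will be assigned". SAP 4 does not say whether imputed dates enter last follow-up, so this is an open question.

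None of this narrows the definition for SAP 6.9.2.1, where nothing else in the SAP corrects the censoring time.

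**Conclusion.** The point holds in a limited form. For time to first opioid, the SAP's definition combined with Protocol 11.6 censors a child withdrawn opioid-free before 72 h at 72 h whenever a safety or adverse event date falls at or after 72 h. The error runs in one direction, towards more opioid-free time, and in the assumed scenario it raises the 72 h opioid-free estimate by a factor of 1.7 to 2. For total dose, the SAP contradicts itself on what triggers projection. The 3-fold gap for one child, and 3.7% to 7.6% in the geometric mean for one or two children in 30, measure the distance between the two readings and not a bias.

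The sizes rest on assumed withdrawal numbers and patterns of use. One might also infer that the arms would be affected unequally because treatment is open-label; that is possible, but nothing in the documents shows it. The consequence is confined to exploratory endpoints and the Group 1 log-rank p-value. The PK and safety objectives are untouched.

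**What to change.** 1. In SAP 4, add an end-of-opioid-observation time for the opioid endpoints: the earlier of 72 h and the end of the period for which opioid use, including none, was recorded. That end is withdrawal, or a later contact that captured opioid use since then. Exclude adverse event dates, safety-only contacts and imputed dates. Keep the existing definition for other purposes.
2. Use this time for censoring in SAP 6.9.2.1, and as both the projection trigger and x in SAP 6.9.2 and 6.1.1.2, with one notation. For the 24 h and 48 h totals, apply the same rule with the interval's own end.
3. Reconcile Protocol 11.6 with 11.6.3, so that it is clear whether analgesics are recorded to 96 h after withdrawal.

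The cost is one added definition, aligned wording in three SAP sections and one protocol clarification. Withdrawal and medication times should already be on file, but for an opioid-free child the record must show explicitly that no use was reported up to the chosen time. The downside is slightly more censoring or projection for a few early withdrawals.
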